6.3 Missing data

To account for missing data in our performance-based and patient-reported outcomes, we will use multiple imputation for our analyses.[42-44] In the Cox proportional hazards analyses for ICU and hospital mortality outcomes, patients with incomplete follow-up will be censored at the time of last contact.

6.4 Additional analyses

Subgroup analyses

We will perform three exploratory *a priori* subgroup analyses to investigate potential treatment effect modification for the primary outcome. All subgroup analyses will be adjusted for age and center.

- i. Age ≥ 65 versus < 65 years.
- ii. Baseline Clinical Frailty ≥ 5 versus < 5 .
- iii. Male versus female.

In separate linear regression models for each of the three subgroup analyses, we will include randomized treatment allocation, the subgroup variable, and the interaction between the subgroup variable and randomized treatment allocation as independent variables. These analyses will be adjusted for age and center. We hypothesize that the treatment effect will be greater for older compared to younger patients [45], greater in patients with frailty compared to those without [45], and greater in males compared to females [46, 47]. For statistical significance in the subgroup analyses, we will use an alpha of 0.10 for the interaction term. We will assess the credibility of any statistically significant subgroup effect using the method of Schandelmaier *et al.*[48] We will report these data in a forest plot.

Sensitivity analyses

To assess the robustness of our findings, we will conduct five sensitivity analyses for our primary outcome. All sensitivity analyses will be adjusted for age and center, unless specified.

- i. To account for ICU mortality on the primary outcome, we will conduct an analysis where we include all patients who died prior to 3-days post-ICU discharge and will assign a PFIT-s score of 0 for those patients.
- ii. We will conduct a linear regression analysis that includes only PFIT-s assessments performed by assessors blinded to treatment allocation.
- iii. We will conduct an analysis where we only include patients with adherence to the protocol on $\geq 80\%$ of planned ICU days. Adherence is defined as either received the randomized intervention or had a temporary exemption.
- iv. We will investigate the effect of missing data by conducting a complete case analysis, including only those patients with a total PFIT-s score at 3 days post ICU discharge.
- v. To determine if the cycling effect is affected by centre, we will conduct analysis adjusting for age only.

See Table 2 for further details.

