3.0 STUDY METHODS

3.1 Trial design

CYCLE (Critical care cycling to improve lower extremity strength) is a 360-patient, international, multi-center, open-label, parallel group randomized trial (1:1 ratio) with blinded primary outcome assessment at 3 days post ICU discharge. Assessors were blinded to treatment group allocation.

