3.3 Sample size

Sample size and power

Our sample size of 360 patients was based on identifying a 1.0 point mean difference[13] between the Cycling and Routine groups for the Physical Function Test for ICU-scored (PFIT-s) measured at 3 days after ICU discharge.[14, 15] Psychometric studies of the PFIT-s identified the minimal clinically important difference was 1.0 points.[14, 16] Logistic regression analysis of patients enrolled in TryCYCLE [7] and the CYCLE pilot randomized study [8] identified that each 1.0 point increase in PFIT-s at ICU discharge (representing better function) was associated with a 40% reduction in the composite outcome of death, readmission to ICU, or requiring paid assistance for activities of daily living at hospital discharge.[13] Based on a standard deviation of 2.5 points at ICU discharge,[7, 17] a 1.0 point difference between groups,[13, 14, 16] and 90% power (0.05 alpha), we need to randomize and analyze 266 patients (133 per group). Based on 66 patients enrolled in the CYCLE Pilot RCT, we anticipated approximately 35% total attrition (25% ICU mortality, 1% mortality in the first 3 days post-ICU discharge, 5% missed primary outcome assessments at 3 days post-ICU, and 5% unblinded). Therefore, we will recruit 360 patients overall.

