4.0 STATISTICAL PRINCIPLES

4.1 Confidence intervals and P values

All statistical tests will be 2-sided and will be performed using a 5% significance level. We will report the two-sided 95% confidence intervals.

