6.2 Analysis methods

Statistical analysis

We will analyze patients according to the group to which they were randomized for all outcomes and will use multiple imputation to handle missing data (see section 6.3). We will summarize

baseline characteristics by group reported as mean (SD) or median (first quartile, third quartile) for continuous variables and count (percent) for categorical variables. The criterion for statistical significance will be set at $\alpha=0.05$ for the Primary Outcome. P-values will be reported to 3 decimal places, with those less than 0.001 reported as $p<0.001$.

Analysis of the Primary outcome

To determine if there is a difference in PFIT-s score at 3 days after ICU discharge between the Cycling and Routine groups, we will conduct a linear regression, including randomization (Cycling vs. Routine) as an independent variable. We will adjust for age (≥ 65 years versus <65 years) and clinical site as these were used as stratification variables in the randomization. We will report the results of the regression as mean difference in PFIT-s with corresponding 95% confidence intervals (CIs) and p-values. We consider a 1-point difference in score clinically important.[14, 16] Although the goal was to have all outcome assessors remain blinded to treatment allocation, this was not always feasible. To maximize use of available data, we will include all PFIT-s measures at 3 days post-randomization, regardless of blinding status of the outcomes assessor and report the proportion of assessments performed by blinded assessors.

To account for incomplete component data in the PFIT-s at 3 days post-ICU, we will concurrently consider data from the PFIT-s, 30s sit-to-stand, and 2-minute walk tests. We will evaluate all PFIT-s data components at 3-days post-ICU. We will identify all patients with any incomplete physical function data and review the scored values for all 4 components of the PFIT-s (i.e., shoulder flexion, knee extension, level of assistance required for the sit-to-stand, and step cadence). In the PFIT-s, a score of “0” represents a lack of physical ability to complete the outcome measure. Thus, if a patient attempted the item and was unsuccessful, the item receives a score of “0”, which is a true 0 (Table 4). See supplementary appendix for further details. Table 2 describes the primary outcome analysis.

Analysis of Secondary outcomes

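### The only planned check on missing day-3 PFIT-s in survivors is a complete-case analysis, which, like the multiple imputation it checks, assumes data missing at random

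*SAP*

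**What the plan says.** The primary analysis covers patients alive 3 days after ICU discharge (SAP 4.3). It is a linear regression of PFIT-s on arm, adjusted for age group and site (6.2).

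Missing scores are handled in 6.3: "To account for missing data in our performance-based and patient-reported outcomes, we will use multiple imputation for our analyses". The SAP names no imputation model, no auxiliary variables and no missingness assumption.

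Two rules turn some incomplete data into scores before imputation:

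- In 6.2, "if a patient attempted the item and was unsuccessful, the item receives a score" of 0.
- Supplement 2 and Table S2 fill some items with 0, or occasionally another value, from other function observed at the same time point.

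Both rules need something to have been attempted or observed. A survivor with nothing recorded on day 3 stays missing and is imputed.

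Of the five sensitivity analyses in 6.4 and Table 2, only iv concerns missing data: "We will investigate the effect of missing data by conducting a complete case analysis". Table 2 expects it to leave the treatment effect unchanged. Analysis i gives a score of 0 to patients who died. Analyses ii, iii and v concern assessor blinding, adherence and site adjustment.

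**The concern.** A sensitivity analysis for missing data is useful when it changes the assumption behind the primary analysis. Analysis iv largely keeps it. Imputation draws the missing scores from a model fitted to assessed patients, while complete-case regression omits the unassessed and lets the assessed stand for them given the covariates. If unassessed survivors score lower, or higher, than the model predicts, and to a different extent by arm, both estimates are biased in the same direction. The report could then present their agreement as robustness to missing data when the relevant assumption was never varied.

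The trial is open-label, so missed assessments could differ by arm. The SAP does not say whether they do.

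**Working it through.** **Inputs from the SAP**

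- SD: "Based on a standard deviation of 2.5 points at ICU discharge" (3.3).
- Target: "90% power (0.05 alpha), we need to randomize and analyze 266 patients (133 per group", for a 1.0-point difference (3.3).
- Test: "All statistical tests will be 2-sided and will be performed using a 5% significance level" (4.1). Allocation is 1:1 (3.1).
- Missing scores: "5% missed primary outcome assessments at 3 days post-ICU" (3.3).
- Deaths before day 3: 25% in ICU plus 1% in the 3 days after (3.3).
- Clinically important difference: 1 point (6.2).

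**Assumptions not in the SAP:** the score gap between assessed and unassessed survivors (1 to 4 points), and the split of unassessed patients by arm.

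**Step 1: the plan's own figure.** Per arm, n = 2 × (1.960 + 1.282)² × 2.5² / 1.0² = 131.4, so 132 (264 in total). The noncentral t calculation gives 133 per arm, 266 in total, with power 0.901. The stated 266 is reproduced.

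**Step 2: how many survivors are unassessed.** Section 3.3 adds its attrition percentages, so I take each as a share of 360. Survivors: 360 × (1 − 0.26) = 266.4, about 133 per arm. Missed: 0.05 × 360 = 18. Share of survivors: 18 / 266.4 = 6.8%.

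**Step 3: scale.** SE = 2.5 × √(2/133) = 0.307. Smallest significant difference = 1.96 × 0.307 = 0.60.

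**Step 4: bias from a departure from missing at random.** If unassessed survivors score g points below what the model predicts, the bias in the mean difference is

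bias = (m_C × g_C − m_R × g_R) / 133,

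where m is the number unassessed in each arm (C cycling, R routine).

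| Unassessed, one arm v other | Gap 1 point | Gap 4 points |
|---|---|---|
| 9 v 9 | 0 | 0 |
| 12 v 6 | 6 × 1/133 = 0.05 | 6 × 4/133 = 0.18 |
| 14 v 4 | 10 × 1/133 = 0.08 | 10 × 4/133 = 0.30 |

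Equal numbers do not guarantee zero bias. With 9 v 9 and a 3-point gap in one arm only, it is 9 × 3/133 = 0.20. With twice the missingness (36) split 24 v 12, gaps of 1 to 4 points give 12 × g/133 = 0.09 to 0.36.

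**Step 5: does complete case reveal it?** Simulation with true effect 0, 133 per arm, a gap of about 3 points, 1,500 trials and 20 imputations gave these mean estimates:

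| Missing by arm | Complete case | Imputation, analysis covariates only | Imputation plus one auxiliary (correlation 0.6) |
|---|---|---|---|
| 6.8% v 6.8% | −0.01 | −0.01 | −0.01 |
| 9.0% v 4.5% | +0.137 | +0.137 | +0.092 |
| 10% v 3.4% | +0.201 | +0.201 | +0.135 |

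The formula agrees with the second row: 6 × 3.07/133 = 0.139, where 3.07 is the simulated gap. Without auxiliaries the two methods carry the same bias. With one auxiliary, imputation keeps about two thirds of it (0.092/0.137 = 0.67).

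**The case against.** Four objections deserve weight.

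- **The imputation model is open.** PFIT-s, muscle strength and sit-to-stand are collected at ICU awakening and ICU discharge, and the 2-minute walk at ICU discharge (Table 3, Supplement Table 1). If imputation uses them, it need not agree with complete case. With a 14 v 4 split and missingness driven by an earlier score correlated 0.6 with the outcome, a simulation put complete-case bias at about 0.16 and imputation bias at about 0. A reader might infer that analysis iv can never detect a problem, or that both methods are always biased by the same amount. The SAP does not support that. The equality is exact only without auxiliaries. What stands is that neither method examines differences beyond the modelled variables.
- **Supplement 2 is consistent.** A reader might see a contradiction between scoring weak patients 0 and imputing patients with no items. There is none: zeros follow observed weakness, and items without enough information are left missing. Imputing a wholly unobserved patient follows the same rule.
- **The reasons are unknown.** Section 3.3 says only that assessments are missed. Illness, readmission or refusal would be inference, and missed tests could equally be logistical or follow early discharge of fitter patients. Section 6.1 chose the PFIT-s because nearly everyone should manage some part of it. The direction of any bias is therefore open.
- **The larger figures are scenarios.** The 4-point gap (1.6 SD) has no source. Under equal missingness, a split at least as uneven as 14 v 4 has two-sided probability 0.03, and 12 v 6 has 0.24.

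None of this supplies an analysis that departs from missing at random for living patients.

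**Conclusion.** The point holds as a gap in the sensitivity analyses. It does not show that the primary analysis is biased. Multiple imputation is a reasonable primary method, but the complete-case analysis is a weak test of it, and the agreement that Table 2 expects would be little evidence of robustness.

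At the planned 5% missed rate the plausible effect is modest: from about 0 to 0.18 points for splits up to 12 v 6, reaching 0.30 only with both an assumed 4-point gap and a 14 v 4 split. That maximum is about one standard error (0.30/0.307), half of the smallest significant difference (0.30/0.60) and under a third of the 1-point important difference. It could move a borderline result in either direction, but could not alone turn a zero difference into a significant one. The conclusion rests on the assumed gaps and splits. More missing data than planned would raise the figures in proportion.

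**What to change.** 1. In 6.3, keep multiple imputation as primary and state its model: arm, age group and site, plus the earlier PFIT-s and strength scores already collected.
2. In 6.4 and Table 2, keep analysis iv but describe it as a descriptive complete-case analysis, not as the test of the missing-data assumption.
3. Add one delta-adjusted (tipping-point) analysis. Shift the imputed day-3 PFIT-s of unassessed survivors over a range such as −4 to +4 points, separately by arm, bounded to 0–10, and report where the conclusion changes. Both directions are needed because the SAP gives no ground for assuming that unassessed survivors do worse. With 18 unassessed, the extreme corner (−4 in one arm, +4 in the other) moves the estimate by at most 18 × 4/133 = 0.54 points.
4. Report the number of unassessed survivors by arm, with reasons where recorded.

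Scoring unattempted tests as 0 is not recommended, because 6.2 reserves a genuine zero for an item attempted without success.

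The cost is a few lines of text and one extra analysis in SAS. It needs no new data and leaves the primary method unchanged. The downside is that the delta range is a judgement and should be fixed before unblinded data are seen.

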6.5 Harms

For the safety analysis, we will only include the days on which the patients received the randomized intervention (i.e., days at risk of a safety event associated with rehabilitation

activities). We will report the frequency and percentage of patients with severe and serious adverse events, by group. We will also report the frequency and percentage of randomized intervention days with severe and serious adverse events, by group.

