3.2 Randomization

Randomization occurred after informed consent was obtained. We concealed allocation and used a central randomization process. We used a web-based, secure randomization service (<http://www.randomize.net/>). After informed consent, the site research coordinator logged in to the website, registered the patient, and received the randomized assignment, ensuring allocation concealment. Patients were stratified by center and age (≥ 65 vs. < 65 years old).

Interventions and comparator

Intervention (Cycling): Patients were randomized to receive 30 minutes/ day of in-bed cycling in addition to routine physiotherapy interventions, 5 days per week, during their ICU stay. Cycling occurred for a maximum of 28 days or stopped when the patient could march on the spot for 2 consecutive days, whichever occurred first.

Comparator (Routine): Patients received routine physiotherapy interventions per current institutional practice. Routine PT included, based on the patient's alertness and medical stability, activities to maintain or increase limb range of motion and strength, in- and out-of-bed mobility, ambulation, and assistance with optimizing airway clearance and respiratory function.[4, 10-12]

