4.2 Adherence and protocol deviations

4.2.1 Adherence

Definitions:

“*Study days*” included all days in ICU from day of randomization up to 28 days post-randomization.

We did not plan for the randomized intervention to occur in the following circumstances:

- On days when a patient was randomized after normal physiotherapist working hours
- On days when a patient was transferred out of ICU before 12:00 pm
- On weekend days or statutory holidays
- For those randomized to in-bed cycling, patients who had marched on the spot for 2 consecutive days (and continued marching or higher mobility for the remainder of their ICU stay)

The remaining days were “*Planned intervention days*”. On weekdays (i.e., Monday through Friday), physiotherapists reviewed study patients for one or more of the following “Temporary exemptions” before offering the randomized intervention:

1. Increase in vasopressor/ inotrope within last 2 hours
2. Active myocardial ischemia, or unstable/ uncontrolled arrhythmia per ICU team
3. Mean arterial pressure <60 or >110 mmHg or per treating team within the last 2 hours
4. Heart Rate <40 or >140 bpm within the last 2 hours
5. Persistent SpO₂ <88% or per treating team within the last 2 hours

6. Neuromuscular blocker within last 4 hours
7. Severe agitation (Richmond Agitation and Sedation Scale >2 [or equivalent][20]) within last 2 hours
8. Uncontrolled pain
9. Change in goals to palliative care
10. Team perception that in-bed cycling or therapy is not appropriate for other new reasons (e.g., acute peritonitis, new incision/wound, known/suspected rhabdomyolysis)

If the patient had no “*Temporary exemptions*”, we offered the randomized intervention.

Each “Planned intervention day” without a “Temporary exemption” was an “*Eligible day*”. An eligible day where a patient did not receive the randomized intervention, was a “*Missed opportunity*”. Missed opportunities may have occurred due to:

1. Patient factors (e.g., patient not available due to a test, or declined)
2. Therapist factors (e.g., therapist not available due to vacation or sickness)
3. Equipment factors for patients in the Cycling arm (e.g., cycle ergometer malfunction)

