We will report the following adverse events if they occurred during or immediately after in-bed cycling or routine physiotherapy interventions, if they were attributable by the clinical team to the randomized intervention, and resulted in a clinical deterioration of the patient's status [3, 7, 39-41]:

Severe adverse events: unplanned extubation, cardiac arrest, or fall to knees during routine PT/ rehabilitation activities.

Serious adverse events: Concern for myocardial ischemia or suspected new unstable/ uncontrolled arrhythmia; Sustained symptomatic bradycardia (<40 bpm) or tachycardia (>140 bpm) and clinical deterioration attributed to in-bed cycling or routine PT/ rehabilitation activities; Sustained hypertension (mean arterial pressure >120 mmHg) and clinical deterioration attributed to in-bed cycling or routine PT/ rehabilitation activities; Sustained O₂ desaturation below baseline and clinical deterioration attributed to in-bed cycling or routine PT/ rehabilitation activities; Marked ventilator dyssynchrony; Bleeding at femoral catheter site attributed to in-bed cycling or routine PT/ rehabilitation activities; New bruising at femoral catheter site attributed to in-bed cycling or routine PT/ rehabilitation activities.

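### The safety day set in SAP 6.5 is defined differently in the two arms: Cycling patients' days of physiotherapy without cycling are left out, which lowers the percentage of Cycling patients with an event if those days carry risk

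*SAP*

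**What the plan says.** SAP 6.5 (Harms) restricts the safety analysis: "For the safety analysis, we will only include the days on which the patients received the randomized intervention". In brackets it explains these as "days at risk of a safety event associated with" rehabilitation activities. It plans two descriptive summaries by group: the percentage of patients with severe and serious adverse events, and the percentage of randomized intervention days with such events.

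SAP 3.2 defines the two interventions. For Cycling: "30 minutes/ day of in-bed cycling in addition to routine physiotherapy interventions". For Routine: "Patients received routine physiotherapy interventions per current institutional practice".

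SAP 4.2.1 lists the days on which the randomized intervention was not planned. One entry applies to a single arm: "For those randomized to in-bed cycling, patients who had marched on the spot for 2 consecutive days" and who kept at least that level of mobility. It also names equipment failure as a reason for a missed day in the Cycling arm only.

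SAP 6.1 lists the events to be reported. The severe group reads "Severe adverse events: unplanned extubation, cardiac arrest, or fall to knees during routine PT/ rehabilitation activities". Several of the serious events are worded so that they may be attributed either to cycling or to routine physiotherapy. The lead-in to the list, however, requires that the clinical team attribute the event to the randomized intervention.

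**The concern.** The rule in 6.5 and its bracketed explanation agree in the Routine arm, where a day of physiotherapy is a day of the randomized intervention. They do not agree in the Cycling arm. There, a day of physiotherapy alone is a day at risk from rehabilitation but, read literally, not a day of the randomized intervention. Such a day and any event on it leave the analysis in one arm and stay in the other.

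This can happen in patients who follow the protocol exactly, because SAP 3.2 itself ends cycling once the patient has marched on two consecutive days. Adherence reporting would therefore not reveal it. The sensitivity analyses in SAP 6.4 concern only the primary outcome, and no harms analysis over all rehabilitation days is planned. At stake is whether the two arms' harm percentages can be compared.

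**Working it through.** The SAP gives no harms figure, so there is nothing to reproduce. The check has two parts: how the text classifies each kind of day, and what follows numerically under equal true risk.

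**Classification of ICU days under the literal rule (SAP 3.2, 4.2.1, 6.5)**

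| Day | Cycling arm | Routine arm |
|---|---|---|
| Cycling plus physiotherapy | counted | not applicable (cycling here is a major deviation, SAP 4.2.2) |
| Physiotherapy alone, cycle unavailable | not counted | counted (ordinary physiotherapy day) |
| Physiotherapy alone, after two consecutive marching days | not counted | counted |
| No rehabilitation | not counted | not counted |

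The middle two rows are the asymmetry. That physiotherapy is given on those Cycling days is an inference: SAP 3.2 stops cycling but does not say that physiotherapy stops.

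**Inputs (all assumptions; none is in the SAP)**

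- D = 8 rehabilitation days per patient in both arms
- p = 0.2% event risk on an ordinary day, the same in both arms
- s = share of Cycling days that are physiotherapy alone
- m = risk on those days relative to an ordinary day

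**Percentage of patients with an event**

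- Routine: 1 − (1 − p)^(D(1−s)) × (1 − mp)^(Ds)
- Cycling as counted: 1 − (1 − p)^(D(1−s))

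Equal daily risk (m = 1), s = 20%:

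- Routine: 1 − 0.998^8 = 1.59%
- Cycling: 1 − 0.998^6.4 = 1.27%
- Ratio 0.80, where the truth is 1.00. In 180 patients per arm (half of 360) the gap is 180 × (1.59% − 1.27%), about 0.6 of a patient.

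Cycling/Routine ratios:

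| s | m = 0.5 | m = 1 | m = 2 | m = 3 |
|---|---|---|---|---|
| 10% | 0.95 | 0.90 | 0.82 | 0.75 |
| 20% | 0.89 | 0.80 | 0.67 | 0.57 |
| 30% | 0.82 | 0.70 | 0.54 | 0.44 |

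Every entry is below 1. The ratio reaches 1.00 only if the dropped days carry no risk at all or no days are dropped. The largest absolute gap in the table (s = 30%, m = 3) is 2.53% against 1.11%, about 2.6 patients in 180.

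The ratio hardly depends on the event rate. With p = 1% and D = 10, Routine is 1 − 0.99^10 = 9.56%. Cycling is 8.65% with 90% of days kept (ratio 0.90) and 6.79% with 70% kept (ratio 0.71).

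**Percentage of days with an event**

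- Routine: (1 − s)p + smp
- Cycling as counted: p
- Ratio: 1 / [(1 − s) + sm]

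| s | m = 0.5 | m = 1 | m = 2 | m = 3 |
|---|---|---|---|---|
| 20% | 1.11 | 1.00 | 0.83 | 0.71 |
| 30% | 1.18 | 1.00 | 0.77 | 0.62 |

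Numerator and denominator shrink together, so there is no bias at equal daily risk. Cycling looks less safe if the dropped days are the safer ones, and safer if they are the riskier ones.

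**After the change.** With the same day set in both arms, equal true risk gives a ratio of 1.00 on both measures.

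**The case against.** A reader might infer that the rule makes Cycling look safer on both planned measures. The documents do not support this. The day-level measure is unbiased at average risk and can go either way otherwise. One listed event, the fall to the knees, may well be commoner once a patient is mobile. Much of the rest of the list concerns the airway, the ventilator, haemodynamics or a femoral catheter, and a patient who has marched for two days could be at lower risk of those. The SAP does not settle which dominates.

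Nor does the SAP support the idea that the dropped days are mostly late, mobile ones. It gives no count of them. A patient must remain in ICU after two marching days for any to arise. Of the three kinds of missed opportunity in SAP 4.2.1, patient and therapist factors apply to both arms and may prevent physiotherapy as well; only equipment failure is specific to Cycling.

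Three further points carry weight. The absolute effect is small when events are rare. The harms analysis is descriptive, with no between-group test planned. An on-intervention safety set is a recognised choice for events tied to a therapy session, and mortality is analysed in all enrolled patients (SAP 4.3), so wider harm is not hidden.

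It can also be argued that the bracketed explanation in 6.5 already points to all rehabilitation days, so that the text is ambiguous rather than wrong. But SAP 4.2.1 treats a cycle malfunction as a reason for not receiving the randomized intervention, which supports the literal reading. An ambiguity of this kind still needs to be settled before the analysis. None of these points removes the asymmetry in the percentage of patients with an event.

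**Conclusion.** The point holds in a limited form. Read literally, 6.5 leaves out Cycling patients' days of physiotherapy without cycling and keeps the same kind of day in Routine, contrary to its own description of the set. If such days occur and carry any risk, the percentage of patients with an event is biased in favour of Cycling. At equal daily risk the ratio falls by roughly the share of days dropped: about 0.90 at 10% and 0.80 at 20%. The absolute difference is small when events are rare. For the percentage of days with an event, no direction can be claimed.

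This rests on three things that the SAP does not state: that physiotherapy continues on days without cycling, what share of days these are, and the daily risk on them. The change is worth making because the bias at patient level is one-sided and easily avoided, but it does not threaten the trial's main conclusion.

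**What to change.** In SAP 6.5, define the safety day set identically in both arms: all ICU study days with any recorded in-bed cycling or routine physiotherapy. Count the recorded listed events on those days by randomized group, for both the patient and the day percentages. Keep the present on-intervention day set as a supplementary analysis, and split the Cycling days into those with and without cycling so that the cycling-specific rate remains visible.

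Do not rewrite the attribution condition in SAP 6.1 retrospectively. Data have been collected under it, so the analysis should be limited to events already recorded. If events on Cycling days of physiotherapy alone were not captured because of that condition, the report should say so. Supplement Table 1 shows study-related adverse events and co-interventions documented daily on case report forms. It does not show whether physiotherapy and events on these particular days were recorded, so this should be checked before the day set is finalised.

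The cost is a change of wording and one extra table. The small downside is that the main Cycling rate is no longer purely a rate per cycling day; the split restores it.
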